Strength - Grip Strength Test (Hamilton, Balnave, & Adams, 1994)

PROMIS measures self-report of emotional functioning (Cella et al., 2007)

Each test in this panel is age normed. Therefore, even though subjects will be of different ages, the change in their performance as a percentage of the normed values will be relevant and comparable from subject to subject. There are also published test-retest standard deviations from which to ascertain how much of a change in score is needed for a change to be regarded as significant.

 Neuro-QOL scale will be collected at each visit. The Neurologic Quality of Life (Neuro QoL) will be collected prior to starting study drug and at each study visit. Descriptive statistics for this measure will be reported in the form of median and range. Mann Whitney U Test will be used to assess whether a significant change in quality of life has occurred after treatment compared to prior to treatment. NeuroQoL will be collected at both sites, KKI and CCHMC, and the de-identified results will be sent to KKI for analysis.

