5.0 Data and Safety Monitoring Plan

The Study Chair ([name]) has primary oversight responsibility of this clinical trial. Based on the determination by the NINDS Safety and Risk Assessment Committee, an NIH appointed Data Safety and Monitoring Board is not required. [name], [name] and the sub-investigators at each site will comprise the Safety Monitoring Committee. The Safety Monitoring Committee will review accrual, patterns and frequencies of all adverse events, and protocol compliance every six months. The Study Chair will provide Safety Monitoring Committee reports and meeting summaries to the NIH program officials regarding the continuation status of the protocol.

[name] and [name] currently speak about weekly and will continue to do so. They will review data together every month for this small pilot trial by 1) Reviewing and analyzing the progress of the study; 2) Monitoring the safety of the study treatments and diagnostic procedures; 3) Ensuring data quality; 4) Recommending early stopping or continuation of the trial (if applicable); and 5) Reviewing recruitment and event rates. They will assess the proportion of enrolled versus projected enrollment and proportion of subjects who have completed the trial.

The research coordinator at each site will make safety calls and/or email/text contact with each participant bimonthly to ensure follow-up and assessment of any adverse events. Also, subjects will be asked to keep daily diaries of any side effects or concerns and asked to email or fax them in on a bimonthly basis. If any adverse events have occurred, the PIs will be notified immediately and corrective actions will take place. While patients with Sturge-Weber syndrome can have serious medical issues, we do not expect any serious adverse events (SAEs) directly attributable to the study drug.

Occurrence of an SAE directly attributable to the study drug will trigger a review to consider stopping the participant on the study within one month of the event. Based on a prior study, an adverse event rate of approximately 0.7 +/- events/subject/month is expected. An adverse event rate more than double this event rate will trigger an indepth review to consider whether to consider continuing the participant on the study; an important consideration in this decision will be whether the adverse events are considered to be due to the study drug or not.

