Vaccination - Immunosuppressants may affect response to the vaccination. Therefore, during treatment with sirolimus, vaccination may be less effective. The use of live vaccines should be avoided; live vaccines may include, but are not limited to, the following: measles, mumps, rubella, oral polio, BCG, yellow fever, varicella, and TY21a typhoid.

Toxicity: We do not expect any serious side effects with the low dose selected for this pilot study. The table below describes toxicities which have been reported for sirolimus over a wide dose range (up to 24 mg/m2 or higher).

Table 3

Table 3					
113	Common	Occasional	Rare		
1	Happens to 21-100	Happens to 5-20	Happens to < 5 children		
	children	children out	out of		
5	out of every 100	of every 100	every 100		
lmmediate:	Headache (L),	Chest pain, insomnia,	Hypotension, asthma,		
Within 1-2 days	hypertension (L),	dysphagia, vomiting,	increased cough,		
of receiving drug	nausea,	dyspnea	flu like syndrome,		
h.	immunosuppression	* *	tachycardia, anorexia,		
1	(L), diarrhea,		sensitivity reactions		
	constipation, fever		1		
	ol va				

Prompt: Within 2-3 weeks, prior to the next course	creatinine/BUN, anemia, asthenia, pain (abdominal, back, pain), hyperlipidemia, hypercholesteremia, hypertriglyceridemia,	leukopenia, hyper/hypokalemia (L), hypophosphatemia, rash, hives, pruritis, hyperuricemia, delayed wound healing, hypomagnesaemia (L)	Gastritis, esophagitis, flatulence, CNS abnormalities: (confusion (L), somnolence (L), depression (L), anxiety, anxiousness, paresthesias, emotional labiality, hypo/hypertonia, dizziness, neuropathy, hypesthesia, nervousness), infections (bacterial, fungal, viral—sepsis, cellulitis, herpes simplex & zoster, EBV, mycobacterial, sinusitis, pharyngitis, abscess, pneumonia, bronchitis, peritonitis), pleural effusions, pleural edema, hypoxia, thrombosis, thrombophlebitis, myalgia
Delayed: Any time later during therapy, excluding the above conditions	Acne		Skin ulcer, hirsutism (hypertrichosis) (L), gingival hyperplasia, abnormal vision, ear pain, cataracts, otitis, tinnitus, hemorrhage, ileus, chronic renal dysfunction, renal tubular necrosis, post-transplant diabetes mellitus (L), CHF, ascites, thrombocytopenic purpura (hemolyticuremic syndrome), arthrosis, bone necrosis, osteoporosis
Late: Any time after completion of treatment			Lymphoproliferative disorders, skin malignancies

Unknown	Sirolimus was embryo/feto-toxic in rats at dosages of 0.1 mg/kg and

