The quantification of the facial birthmark score developed and validated at the KKI will occur at the beginning of the study, prior to starting study drug, and when the subjects reach the endpoint of the study at six months' time while still on the study drug (Waelchli et al., 2014). If the subject elects to enter the Extension Phase, the facial birthmark will be rated at each Extension Phase visit. Descriptive statistics for this measure will be reported in the form of median and range. Mann Whitney U Test will be used to assess whether a significant change in the facial birthmark has occurred after treatment compared to prior to treatment. Facial birthmark scoring will occur at both sites, KKI and CCHMC, and the de-identified results will be sent to KKI for analysis.

- hCG urine pregnancy test will be used for all female participants Tanner stage 2 (see Study Visit Table) and above. We will tell subjects that they must use adequate contraceptive measures, which may include abstinence, contraceptive implants, and condoms, but may not include estrogen containing contraceptives. We will confirm that this is the case each time they complete our clinic/telephone monitoring script. We will inform female subjects that they should not become pregnant or breastfeed a baby while on this pilot study or for 12 weeks after taking sirolimus. We will also inform male subjects that they should not get their partners pregnant while on this study or for 12 weeks after taking sirolimus. Anyone who becomes pregnant while on the pilot study will be removed immediately. All female subjects of childbearing potential will have a pregnancy test done at each study visit.

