Based on prior experience, the risk of serious toxicity increases at serum levels great than 30 ng/dl. Blood samples will not be shipped between sites. Samples will be collected at each location and taken immediately to the respective lab for measurement of sirolimus levels. The two pathology labs (one at Hopkins and another at CCHMC) have communicated and confirmed they use comparable methods of measuring sirolimus levels.

The lab at Hopkins has confirmed they measure sirolimus using liquid chromatography-mass spectrometry (LC-MS). This analysis is performed after protein precipitation of the sample using an acetonitrile/methanol/zinc sulfate solution containing isotopically labeled sirolimus. The CLIA license number is 21D0680509 for the Hopkins lab. The assay range is 1.6-48.0 ng/mL with an LLOQ of the assay being 1.6 ng/mL and a between-batch variability percentage (%CV) of 6-9% for low, mid, and high QC.

The lab at CCHMC has confirmed sirolimus whole blood concentrations will be determined by a validated routine clinical assay accredited by the College of American Pathologists (CAP license #1667801) and with Clinical Laboratory Improvement Amendments certification (CLIA 88 license #36D0656333). The assay will be performed under GLP principles using LC-MS/MS on a Waters Quattro Micro API triple quadrupole mass spectrometer (Milford, MA) interfaced with Acquity UPLC instrument. The assay range is 0.5-100.0 ng/mL. The LLOQ of the assay is 1.0 ng/mL and within and between-batch variability (CV) is 12.8% and 14.0 %, respectively.

- Lipid panel, CBC, LFT, BUN, creatinine levels, electrolytes, urine protein, sirolimus levels, and levels of other AEDs will be measured at each scheduled visit after study drug is started.
- EEG will be done at baseline and after six months on study drug. Quantitative EEG analysis will be done with this EEG data. An EEG will be done prior to starting the

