5.7 Subject Discontinuation

All data acquired prior to termination for the reasons outlined below will be included in the primary analysis unless patient withdraws consent. Every effort will be made to conduct a final study visit with the participant and participants will be followed clinically until, if applicable, all adverse events resolve.

- Withdrawal of consent
- Withdrawal by the participant
- Withdrawal by the investigator
- Intercurrent illness or event that precludes further visits to the study site or ability to evaluate disease (for example, mental status change, large pleural effusion, large stroke).

Early Stopping Rules: If a participant experiences a significant decline in his or her health or wellbeing, the PIs may remove the participant from the pilot study. This decision will be promptly made on a case-by-case basis with careful discussion between the PIs, the parents and/or patient, and in consultation with the IRB. In some cases, it can be more medically destabilizing to remove the subject from the study drug. However, in any case where a significant decline in health may be attributable to the study drug, or in any case where it is determined that it may not be in the subject's best interest to remain on the study drug, then they will be removed from the study. A significant decline in health or wellbeing could include a loss of seizure control and/or the occurrence of intolerable side effects. Loss of seizure control is defined as an increase in seizure frequency and/or severity or use of emergency medications that warrant the initiation of a new seizure medication or treatment such as, Ketogenic/Atkins diet, surgery, or VNS. If there has been a loss of seizure control, then the subject will be removed from the study drug at that time, he or she will complete the ending assessments, and then the subject will be removed from the trial. Other stopping criteria are listed in Tables 1 and 2 above. Other removal criteria include: death, lost to follow-up, withdrawal of consent for any further data submission, or inability to complete follow up two years from the protocol completion. Early withdrawals within the first two months on the study drug will be replaced with a new study subject.

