8.3 Risks

The primary risk to the subjects from participation in this trial is from sirolimus. Risk of toxicity has been correlated with serum levels of sirolimus and at the low dose range being used in this study, the risk of toxicity is low. All participants will have serum levels

measured regularly to guide appropriate dosing and to minimize toxicity. Participants enrolled in this trial will be carefully monitored for the development of toxicities, with guidelines for discontinuation of drug and stopping rules in place. Please see section 5.3 for more detail and for protocol stopping rules.

We will obtain institutional review board approval at all participating sites. Patients' risks of participating in research will be kept to a minimum with measures to protect confidentiality and planned interim analysis for safety monitoring after 5 subjects have completed the study and continuous assessment of all serious adverse events at all times. Confidentiality will be maximized by coding patient information prior to transfer of data or samples between sites. The treating physician at the clinical center will keep a list linking codes with patient identifying information in accordance with their institutional IRB guidelines. Best of care will be provided to patients in the event of toxicities associated with treatment. Parents will be provided appropriate contact number(s) for treating physicians at clinical sites in accordance with institutional IRB guidelines. For additional risk information, please refer to section 5.3.

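### The protocol sets a 12-week pregnancy-avoidance period after sirolimus but requires no contact with completers after their last dose, so post-dose safety is not actively ascertained

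*Combined protocol and SAP*

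**What the plan says.** Safety and tolerability is listed first among the primary outcome measures in the Synopsis. On the period after treatment, the protocol says the following.

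- **Pregnancy advice (5.3, laboratory tests and clinical procedures).** Female subjects are told that they "should not become pregnant or breastfeed a baby while on this pilot study or for 12 weeks after taking sirolimus". Male subjects are given the same 12 weeks with respect to partners. Table 3 gives a reason: "Sirolimus was embryo/feto-toxic in rats at dosages of 0.1 mg/kg and" above.
- **Pregnancy checks (5.3).** Tests are done at study visits. Contraception is confirmed when the clinic or telephone script is completed. The only action stated for a pregnancy is removal of a subject who conceives during the study.
- **Contraception (4.1, criterion 7).** The requirement covers the time on study drug only.
- **Endpoint timing (5.3).** The six-month EEG and birthmark assessments are made before the drug is stopped. The Extension can add up to 18 months of treatment.
- **Routine safety contact.** Section 4.6 shows monthly safety calls. Section 5.0 describes bimonthly contact and adds that "subjects will be asked to keep daily diaries of any side effects or concerns". Section 8.3 promises "continuous assessment of all serious adverse events at all times". None gives a stopping point.
- **Off-drug follow-up.** Section 5.3 provides it for subjects removed for toxicity. Section 5.7 provides a final visit, and follow-up until adverse events resolve, for listed reasons of early termination. Completion is not one of them.

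**The concern.** The protocol identifies a risk that lasts 12 weeks beyond the last dose, instructs subjects about it, and then requires nobody to find out what happened. A completer whose last contact is on drug could conceive, have a change in seizures, or have a non-serious event in the following weeks without being asked about it. A completer with an adverse event still open at the last dose also lacks the written follow-up to resolution that section 5.7 gives to early terminations.

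At stake are subject safety within the protocol's own risk window and the completeness of a primary outcome. Informal contact may fill part of the gap, but it would be neither uniform across the two sites nor certain to be recorded on study forms.

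**Working it through.** The 12-week period is a stated rule without a derivation, so there is no figure to reproduce. The check is mainly textual, with a short calculation to place the first call.

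**Step 1. Every provision that might reach a completer after the last dose**

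- Schedule of Events (4.6): Visit 6 at week 26, then one Extension column at week 38. There is no off-drug column. This is weak evidence, because section 5.3 refers to Extension visits in a way that implies more than one, so the table is compressed.
- Monthly calls (4.6), bimonthly contacts and diaries (5.0): no end stated and no tie to the last dose.
- Serious-event assessment (8.3): open-ended, but names no contact.
- Pregnancy tests and contraception checks (5.3): each occurs only if there is a visit or a scripted call.
- Toxicity removals (5.3) and early terminations (5.7): off-drug follow-up exists, but not for completers.
- Section 5.7 lists "inability to complete follow up two years from the protocol completion" among the removal criteria. It suggests some later follow-up but attaches no visit, call or content to it.
- Adverse-event definition and reporting (5.2, 5.4, 5.5): no collection window. Section 5.2 defines an event by association with participation, not by being on drug, and the section 5.4 clock starts when the site learns of the event.

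Result: required post-dose contacts for completers, none stated; pregnancy-avoidance period, 12 × 7 = 84 days.

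**Step 2. When should the first call fall?**

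Input: half-life 79 ± 12 h with normal hepatic function (5.3, Drug Information), so 67 to 91 h. Five half-lives in days = 5 × half-life ÷ 24.

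- 67 h: 5 × 67 ÷ 24 = 14.0 days
- 79 h: 5 × 79 ÷ 24 = 16.5 days
- 91 h: 5 × 91 ÷ 24 = 19.0 days

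A call at 30 days leaves at least 30 − 19.0 = 11.0 days beyond five half-lives. It covers any half-life up to 30 × 24 ÷ 5 = 144 h. The 113 h mean quoted for impaired hepatic function gives 5 × 113 ÷ 24 = 23.5 days, still inside 30, and criterion 9 requires adequate liver function. Section 5.3 notes that enzyme-inducing anti-epileptics usually increase sirolimus metabolism, which would shorten these times.

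**Step 3. Who is concerned by the pregnancy check?**

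Table 4 anticipates 5 female subjects out of 10. Ages run from 3 to 31 and testing starts at Tanner stage 2, so fewer than 5 may be at risk. Partners of male subjects are additional.

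**The case against.** The strongest reply is that the plan leaves an end date unstated but does not say that follow-up stops. The calls, contacts, diaries and serious-event assessment carry no cut-off at the last dose, and sections 5.2 and 5.4 make any post-dose event that a site hears of reportable. Participants are the investigators' own patients (4.3), so serious events would often surface. The telephone script and the full Extension schedule are not reproduced in the protocol. All of this stands, and it limits the point to active ascertainment. It does not supply a required contact.

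A second reply is that criterion 7 and section 5.3 do not conflict, because one is an eligibility condition and the other is counselling. That is fair as far as contradiction goes. The two periods still differ, and the eligibility condition states the shorter one.

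Three stronger readings are tempting and should be resisted.

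- A reader might infer that post-dose events will be lost. The documents do not show this, and the share that would be missed cannot be estimated from them.
- A reader might take the sentence "In some cases, it can be more medically destabilizing to remove the subject from the study drug" in section 5.7 as evidence of a withdrawal effect on seizures. Its context is a participant already in significant decline; it says nothing about stable completers.
- A reader might read the missing off-drug column in section 4.6 as proof that no contact will occur. The compressed table cannot bear that weight.

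**Conclusion.** The point holds in a limited form. For subjects who complete the core or Extension phase, no post-dose contact is required, while the protocol's own pregnancy-avoidance instruction runs for 84 days after sirolimus and safety is a primary outcome. What is not assured is active ascertainment of non-serious events, seizure change and pregnancies.

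Its size is modest. At most about 5 female subjects, plus partners of male subjects, are concerned by the pregnancy window. Drug exposure after the last dose is lower than the exposure already monitored, so no large toxicity yield is claimed. The six-month cognitive, EEG and birthmark analyses are unaffected. The conclusion rests on the text as available, and on the stated half-life for the choice of 30 days. It does not depend on any assumed off-drug event rate. The change is recommended because it is cheap and checks a risk period that the protocol sets for itself.

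**What to change.** Amend the protocol as follows.

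1. Using the existing telephone script and the adverse-event and seizure forms, add one call about 30 days after the last dose and one at 12 weeks. Record pregnancy status, including partners' pregnancies, at the 12-week call.
2. Make the calls for every treated subject, so that one rule applies to all, including subjects who leave early and are replaced under section 5.7 ("Early withdrawals within the first two months on the study drug will be replaced with a new study subject").
3. Include events up to 30 days after the last dose in the safety summary, and report later ones separately.
4. Extend the contraception period in criterion 7 (section 4.1 and the Synopsis) to 12 weeks after the last dose, to match section 5.3.

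Cost: one amendment and two calls per treated subject by the existing coordinators. That is 2 × 10 = 20 calls, or 2 × 11 = 22 to 2 × 13 = 26 if one to three early withdrawals are replaced (an assumption). No visit is added. The downside is a few off-drug events that will be hard to attribute. The calls are not meant to detect the rare late malignancies listed in Table 3.

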5.4 Reporting Timeline

- Within 24 hours (of learning of the event), investigators must report any reportable Serious Adverse Event (SAE) that:
 - 1. Is considered life-threatening/disabling or results in death of subject -OR-
 - 2. Is Unexpected/Unanticipated
- Investigators must report all other reportable SAEs within 5 working days (of learning of the event).
- All other (suspected) reportable AEs must be reported to the RDCRN within
 14working days of the notification of the event or of the site becoming aware of the event.

Local institutional reporting requirements to IRBs, any GCRC oversight committee and the FDA, if appropriate, remain the responsibility of the treating physician and the Study Chair.

5.5 RDCRN Adverse Event Data Management System (AEDAMS)

Upon entry of a serious adverse event, the DMCC created Adverse Event Data Management System (AEDAMS) will immediately notify the Study Chair, site PIs, the Medical Review Officer, and any additional agencies (if applicable- industry sponsor, CTEP, etc) of any reported adverse events via email.

Serious adverse events: The NIH appointed Medical Review Officer (MRO) determines causality (definitely not related, probably not related, possibly related, probably related, definitely related) of the adverse event. The MRO may request further information if necessary and possibly request changes to the protocol or consent form as a consequence of the adverse event. A back-up notification system is in place so that any delays in review by the MRO beyond a specified period of time are forwarded to a secondary reviewer. The Adverse Event Data Management System (AEDAMS) maintains audit trails and stores data (and data updated) and communication related to any adverse event in the study.

Non-serious expected adverse events: Except those listed above as immediately reportable, non-serious expected adverse events that are reported to or observed by the investigator or a member of his/her research team will be submitted to the DMCC in a timely fashion (within 20 working days). The events will be presented in tabular form and given to the MRO on a bi-annual basis. Local site investigators are also required to fulfill all reporting requirements of their local institutions.

The DMCC will post aggregate reports of all reported adverse events for site investigators and IRBs.

